12.5 Potential benefits

The study will contribute to our understanding of how to deliver education and counseling to help women and families. It will also provide information that can be used to improve services to ensure more women attend clinic visits, get help with their delivery, and are provided with family planning options. It may help get more babies immunized. The study will also shape future SMS programs. Participants in the intervention arm may personally benefit from having access to advice about infant health and infant illness. It may lead to improved care of the infants, better identification of infant illness and more appropriate care-seeking.

12.6 Compensation

A nominal travel reimbursement will be provided for participant travel to the study clinic (see section 11.6).

12.7 Importance of the knowledge to be gained

This study will determine the efficacy of 2-way communication to improve neonatal and maternal postpartum outcomes.

13. DATA MANAGEMENT

IDIs

IDI audio recordings and transcripts will be uploaded to a password-protected computer and erased from the recorder within one day of interview. Recordings will be erased once transcripts have been validated, no more than 6 months after generation of the recording.

Questionnaires

All questionnaires will be administered using the tablet-based ODK platform. Tablets will be password-protected and questionnaires will be transmitted to a secure server daily and erased from the tablets. Data will be transmitted via secure socket layer (SSL) and only accessible by authenticated users. Tablets will be stored in a secure, locked office accessible to study staff only. All participants will be assigned a non-identifiable study ID number upon enrolment. All data records will be identified by study ID only. The link between identifiable participant information and study IDs will be locked in a secure, locked location and destroyed following study completion. Study analysts will receive only coded data.

Paper records

Consent forms and participant locator information will be stored in paper forms. These will be stored in a secure, locked location and destroyed following study completion.

Data Ownership

The proposed project is a collaborative effort between investigators at the UW and KNH. The aforementioned institutions will jointly share ownership of the data. Study investigators at the UW and KNH will have full access to the data. Authorship on publications, conference presentations, abstracts and other materials generated from this study will reflect contribution to design, execution and analysis of the study.

Data Release/Sharing Policy

This study will comply with the [NIH Public Access Policy](#), which ensures that the public has access to the published results of NIH funded research. It requires scientists to submit final peer-reviewed journal manuscripts that arise from NIH funds to the digital archive [PubMed Central](#) upon acceptance for publication.

14. RESULTS DISSEMINATION

We will establish 4 community advisory boards, one for each facility. This will include medical providers and community members living in the area. We will disseminate results to this board twice a year and ask for guidance if community issues arise.

Study findings will be shared with the participating facilities and Kenyan Ministry of Health at its conclusion as a presentation or written report. Findings will be disseminated to the research community in the form of conference presentations and journal articles.

15. STUDY LIMITATIONS

[figure not shown]
SMS alone cannot directly improve the health care system or address the third delay in care (delay in receiving quality care). There are many other external factors – partner, socioeconomic factors, quality of facility-based care – that may not be modulated by SMS messaging. This may limit our ability to detect an impact on the primary outcome of neonatal mortality. Evaluation of the impact of SMS on secondary outcomes of ENC, knowledge of warning signs, care seeking and maternal mental health will nonetheless enable us to assess whether the SMS intervention has the desired impact and has potential to improve mortality in combination with additional health systems strengthening. Moreover, these **secondary outcomes have value in improving neonatal and maternal health in their own right**. Fidelity and generalizability of dialogue interventions are challenging. We have extensive experience in standardizing messaging dialogue, but it will not be possible to completely standardize the nurse responses in the intervention. This challenge however is part of routine medical care and any type of behavioral interventions involving health workers. Implementation and evaluation in four sites will increase the generalizability of any measured effect. With regards to the care seeking outcome, babies in the control arm may have higher numbers of clinic visits and/ or hospitalizations if their mothers are less likely to practice ENC or if mothers seek care later in the illness process. If we observe this effect we will compare illness severity at presentation between the two arms using a validated neonatal illness assessment. Women in the trial cannot be blinded to their assignment, which may lead to performance bias. Additionally, outcomes obtained by self-report could introduce bias for social desirability, but this will likely occur across all arms.

16. STUDY TIMELINE

The study timeline is summarized in Figure 11. We anticipate that this study will take 5 years to complete. In the first year, we will obtain ethical approval from institutional review boards at the University of Washington and Kenyatta National Hospital. During this time, we will develop and refine study tools and finalize standard operating procedures and publish the clinical trial protocol. We will also adapt the messaging platform technology based on final pilot project data and finalize the message bank for the intervention. Following IRB approval, field site preparation will take 3 months, including hiring and training of site staff, and conducting of mock enrolments and messaging. We will also conduct community sensitization and outreach to ensure the community is aware of the purpose of the project. We will recruit and enroll participants and conduct follow-up over a 24-month period.

The last follow-up visit will occur in quarter 1 of year 4. We will conduct the post RCT interviews in Year 4. Approximately 6 additional months will be needed for data verification and cleaning, ascertainment and transcription of any outstanding clinical records. Data analysis and dissemination including manuscript submissions will occur in Years 4-5.

Figure 11. Study timeline

APPENDIX I COVID-19 RESPONSE PROCEDURES

In response to the COVID-19 pandemic and policy changes issued by the Kenyan Ministry of Health (MOH), we are ensuring study procedures protect the health and safety of study participants and staff. Study visits align with routine patient clinical care schedules, and all participants and staff will follow MOH guidelines within the facility to reduce risks of potential exposure i.e. use of personal protective equipment, appropriate distancing with participants, reducing contact with commonly touched surfaces, handwashing and environmental cleaning. We will provide participant reimbursement via M-PESA to minimize touch points between staff and participants. All data will be collected by study staff on tablets to which only they will have access and will follow disinfection procedures. Participants will not be required to touch any study materials.

Revisions to Data Collection Procedures

Any in-person home visits for follow-up or infant verbal autopsy, or clinic visits for in-depth interviews will be suspended until social distancing measures have been rescinded by the Kenyan government. Follow-up data collection will occur via study visits aligned only with routine clinical care or phone as already noted in this protocol. Verbal autopsies and in-depth interviews will be conducted via phone until in-person study-specific visits are approved by appropriate authorities.

## 1. STUDY SUMMARY AND AIMS

### Rationale:

Globally, approximately half of the estimated 6.3 million under-5 deaths occur in the neonatal period (within the first 28 days of life) and 75% of neonatal mortality occurs in the first week of life. Most neonatal deaths can be averted by existing interventions that prevent and treat neonatal illness. The “three delays framework” identifies 3 critical delays in accessing care: 1) identifying illness and the decision to seek care, 2) reaching an appropriate facility, and 3) receiving adequate care. The first delay occurs beyond the reach of the clinic and is estimated to account for up to 80% of neonatal deaths. **A critical gap exists in supporting caregivers, typically mothers, to implement essential newborn care practices (ENC) at home, identify neonatal illness when it occurs, and seek timely clinic-based care.**

Two-way (interactive) short message service (SMS) offers an efficient way for mothers to remotely interact with a healthcare worker and receive real-time education, counseling, encouragement, and decisional guidance, without placing significant burden on resource-limited health systems. **We hypothesize that two-way SMS in late pregnancy and the neonatal period can reduce neonatal mortality by 1) supporting maternal implementation of ENC (early and exclusive breastfeeding, cord care, and thermal care), 2) improving identification of neonatal danger signs and care seeking, and 3) augmenting maternal social support and self-efficacy, and reducing depressive symptoms** (Figure). We have developed a unique two-way SMS platform (Mobile WACh NEO, MWN) that rapidly and innovatively engages mothers in pregnancy and postpartum care. Our overarching aim is to determine the effect of MWN on neonatal mortality and understand the mechanisms by which this innovation impacts neonatal health. **We propose to determine the effect of MWN on neonatal mortality, ENC, care seeking, and maternal mental health in the first 6 weeks postpartum, in a 2-armed randomized controlled trial (RCT), comparing MWN SMS versus no SMS control.** Our specific aims are:

**Design:** A 2-arm, parallel assignment, unblinded, 1:1 randomized clinical trial (RCT) comparing the effects of MWN bidirectional SMS dialogue between participant and provider vs. control (no SMS) among Kenyan women.

**Population:** Pregnant women ≥14 years old and 28-36 weeks gestation.

**Sites:** Bondo District Hospital (Siaya County), Rachuonyo District Hospital (Homa Bay County), Mathare North City Council Clinic (Nairobi County), Riruta Health Centre (Nairobi County).

**Sample Size:** 5,000 pregnant women will be randomized (2,500 per arm)

**Duration:** Follow-up through 6 weeks postpartum.

### Specific Aims:

**Aim 1: To determine the effect of tailored, systematic two-way MWN SMS on neonatal mortality.**

*Hypothesis: Women randomized to MWN will have lower neonatal mortality than women randomized to control.*

**Aim 2: To determine the effect of MWN SMS on maternal implementation of ENC and care seeking behavior.**

2a. To compare practices of early and exclusive breastfeeding, cord care and thermal care among mothers randomized to MWN versus control.

2b. To compare knowledge of infant danger signs and care seeking for neonatal illness among mothers randomized to MWN versus control.

*Hypothesis: Implementation of ENC, knowledge of neonatal danger signs, and clinic attendance will be higher in mothers randomized to MWN than control.*

**Aim 3: To determine the effect of MWN SMS on longitudinal maternal social support, self-efficacy and depression among mothers randomized to MWN versus control.**

*Hypothesis: Maternal self-efficacy and social support will be higher and depression will be lower among women randomized to MWN than control.*

## 2. STUDY ENDPOINTS

Primary study endpoints:

1. **Neonatal mortality** will be defined as death of a live-born infant within 28 days of birth, based on mother's report, verbal autopsy, or clinic records.

Secondary endpoints:

1. **Early neonatal mortality** will be defined as death of a live-born infant within 7 days of birth, based on mother's report, verbal autopsy, or clinic records.
2. **Initiation of early breastfeeding** will be defined as initiation of breastfeeding within the first hour of life, based on maternal self-report at 2-week postpartum study visit.
3. **Cessation of exclusive breastfeeding** in the first 6 weeks of life will be ascertained based on maternal self-report at the 2-week and 6-week visits.
4. **Bath** in the first 24 hours of life will be ascertained based on maternal self-report at the 2-week visit.
5. **Application of substances to cord** will be ascertained based on maternal self-report at the 2-week visit.
6. **Maternal provision of Kangaroo Mother Care (KMC)** will be defined as proportion of mothers with low birth-weight or preterm babies (<2500g or <37 weeks EGA at birth) who report the baby spent any time skin-to-skin with an adult on  $\geq 10$  of the first 14 days at home.
7. **Maternal knowledge of neonatal danger signs** will be defined as the number of the 8 neonatal danger signs correctly named at 2-week and 6-week visits.
8. **Appropriate care seeking** will be defined as the proportion of illness episodes with danger signs where the infant attended the clinic and/or where the infant was hospitalized independent of neonatal danger signs in the first 18 weeks of life (study follow-up period). Illness episodes are based on maternal self-report and only include the most recent illness episode reported at the 6-week visit or 2-week visit if 6-week data is unavailable.
9. **Elevated depressive symptoms** will be defined as a score  $\geq 13$  on the Edinburgh Postnatal Depression Scale (range 0-30) at 2-week and 6-week visits.
10. **Social support score** will be defined by MOS social support score (range 0-100) at 2-week and 6-week visits.
11. **Self-efficacy** will be defined by the Karitane Parenting Confidence Scale score (range 0-45) at 2-week and 6-week study visits.

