**Table 3.1 Summary of detectable differences**

Indicator	Outcomes (control)	Minimum detectable difference		
		Outcomes (intervention)	Absolute difference	Relative difference
Neonatal mortality per 1000 births 	25.0	13.8	11.2	0.55
	23.0	12.2	10.8	0.53
	20.0	10.0	10.0	0.50
Initiation of BF within 1h; EBF for 6 weeks 	90.0%	93.1%	3.1%	1.03
	80.0%	84.2%	4.2%	1.05
Application of substances to cord; Bath within 24h 	40.0%	45.4%	5.4%	1.14
	50.0%	55.5%	5.5%	1.11
Provision of KMC 	30.0%	43.7%	13.7%	1.46
	25.0%	38.2%	13.2%	1.53
Number of clinic visits in first 6 weeks 	0.50	0.61	0.11	1.22
	1.00	1.11	0.11	1.11
Number of danger signs correctly named 	3.00	3.11	0.11	1.04
	5.00	5.11	0.11	1.02
Maternal depression 	19.0%	14.5%	4.5%	0.76
Maternal social support score; Maternal self-efficacy score (max 4.0) 	2.50	2.61	0.11	1.04
	3.50	3.61	0.11	1.03

 $\alpha$ =0.05, Adjusted  $\alpha$ =0.0045,  $\beta$ =0.8, 2-sided tests

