**Table 5.2 Summary of statistical analyses**

Outcome	Indicator	Timing	Statistical Analysis
Primary outcome			
Neonatal mortality	Death during 1 st 28 days of life	2 and 6 week visits, clinic record abstraction	Log-binomial regression
Secondary outcomes			
Early neonatal mortality	Death during 1 st 7 days of life	2 and 6 week visits, clinic record abstraction	Log-binomial regression
Initiation of early breastfeeding	Breastfeeding in 1 st hour of life	2 week visit	Log-binomial regression
Exclusive breastfeeding	Cessation of EBF in 1 st 6 weeks of life	2 and 6 week visits	Cox proportional hazards
Thermal care	Bath in 1 st 24 hours of life	2 week visit	Log-binomial regression
Cord care	No application of substances to cord	2 week visit	Log-binomial regression
Home provision of KMC	Any duration of skin-to-skin care on ≥10 of the first 14 days at home, among low birthweight or preterm infants	2 and 6 week visits	Log-binomial regression
Maternal knowledge of neonatal danger signs	Number of the 8 danger signs or symptoms successfully named	2 and 6 week visits	Poisson GEE
Appropriate care seeking	Proportion of illness episodes with danger signs where the infant attended the clinic and/or where the infant was hospitalized regardless of danger signs reported in study follow-up	2 and 6 week visits, ongoing record abstraction	Log-binomial regression
Depression	Score above diagnostic threshold (≥13) for Edinburgh Postnatal Depression Scale	Baseline, 2 and 6 week visits	Log-binomial GEE
Social support	Score using MOS Social Support Survey	Enrollment, 2 and 6 week visits	Linear GEE
Self-efficacy	Score using Self-efficacy in Infant Care Scale	Baseline, 2 and 6 week visits	Linear GEE

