**Table 5.3 Study endpoints: shell table**

	Overall	Control	SMS	p-value
Aim 1				
* Neonatal mortality (per 1000 live births)				
Aim 2				
* Early neonatal mortality (per 1000 live births)				
\$ Time to introduction of complementary food				
* Breastfeeding initiated within 1 hour (%)				
* Bathed within 24 hours (%)				
* Substances applied to cord (%)				
* Provision of KMC among LBW/PTB infants (%)				
^ Number of danger signs identified				
+ Proportion of illness episodes with danger signs or hospitalization				
Aim 3				
+ Elevated depressive symptoms (%)				

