Appropriate care-seeking outcome definition & analysis	20 April 2023	3.3	
 
Proportion of illness episodes with danger signs in which infant attended the clinic and/or infant was hospitalized independent of neonatal danger signs in the first 6 weeks of life Analyzed by log-binomial GEE
 
	
 
Proportion of illness episodes with danger signs in which infant attended the clinic and/or infant was hospitalized independent of neonatal danger signs during the study period (up to 18 weeks). If data is unavailable at the 6-week visit, data from the 2-week visit will be used. Analyzed by log-binomial regression
 
	Data collection error resulted in care-seeking only being collected for the most recent illness episode. 6-week visits could occur up to 18 weeks postpartum and we elected to include all data reported at study visits, regardless of when the care-seeking event occurred.
Approach to missing data	14 August 2023	3.4	Sensitivity analyses	Variables with >10% missingness will be imputed by multiple imputation by chained equations (MICE).	Two outcomes and one adjustment variable were found to have high levels of missingness. Multiple imputation has been shown to lead to less biased results than complete case analysis, and allows preservation of sample size.

Approach to exclusive breastfeeding cessation analysis	11 December 2023	3.5	Cox regression	For data imputed by MICE, use Poisson regression with time offset	Implementation of Cox regression with imputed data was unclear and Poisson regression is asymptotically equivalent.
Use of log-binomial vs Poisson regression	11 December 2023	3.5	Log-binomial regression	If any log-binomial regressions fail to converge, we will instead use Poisson regression with robust standard error	Log-binomial regressions frequently fail to converge. Poisson regression with robust standard errors yields asymptotic results.

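### The care-seeking endpoint counts admissions without danger signs as automatic successes and lets the intervention change who enters the denominator, so the ratio can move without a change in care seeking

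*SAP*

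**What the plan says.** SAP Section 2 defines appropriate care seeking in these words: "proportion of illness episodes with danger signs where the infant attended the clinic and/or where the infant was hospitalized independent of neonatal danger signs". The period covered is 18 weeks from birth. Section 5.3 repeats this. Tables 2.1 and 5.2 agree, the latter counting episodes "where the infant was hospitalized regardless of danger signs reported in study follow-up". No section writes out numerator and denominator separately. The nearest is the row label in shell Table 5.3: "Proportion of illness episodes with danger signs or hospitalization".

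Episodes are self-reported by the mother and "only include the most recent illness episode reported at the 6-week visit or 2-week visit if 6-week data is unavailable". Table 6.1 (20 April 2023) explains that 6-week visits could take place as late as 18 weeks and that all reported data were kept, "regardless of when the care-seeking event occurred". Elsewhere, SAP Section 1 and Protocol Section 10.1 place the aim in the first 6 weeks postpartum, and Protocol Section 11.6 ends the intervention at 6 weeks.

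The trial is unblinded. The SAP rationale expects the SMS to work partly by "improving identification of neonatal danger signs and care seeking", and Table 6.1 (31 January 2023) states that the intervention messages discussed the 8 signs used in the knowledge endpoint.

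For power, Section 3c and Table 3.1 still carry "Number of clinic visits in first 6 weeks", which belongs to the earlier count outcome.

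**The concern.** There are three separate difficulties.

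- **Automatic successes.** Admission is both what brings an infant without danger signs into the measure and what makes that infant a success. The matching failures, ill infants without danger signs who were not admitted, are never counted. If such admissions differ between arms for any reason, the ratio moves even when mothers facing danger signs behave identically.
- **A denominator formed after randomisation.** An episode counts when the mother reports danger signs. Mothers in one arm are taught those signs. If they recognise or label more episodes, and the added ones are less often taken to care, the proportion falls. If better newborn care prevents illness, the denominator shrinks. Neither is a change in response to a given illness.
- **Timing.** A late 6-week visit brings in illness well beyond the neonatal period and beyond delivery of the intervention. Because only one episode is kept, a later illness takes the place of an earlier one that the 2-week visit had already captured.

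This is the only endpoint that addresses the care-seeking half of Aim 2b, so a ratio that is hard to interpret leaves that half weakly answered.

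**Working it through.** **The plan's own figure.** Section 3c gives a detectable difference of 0.11 visits (0.50 vs 0.61) with 2,500 per arm, 10% attrition, two-sided alpha 0.0045 and 80% power. Analysed n = 2,500 × 0.9 = 2,250 per arm. No SD is stated. With SD = 1 assumed, (2.841 + 0.842) × √(2/2,250) = 0.110, and power at 0.11 is 0.802. The figure reproduces, but it describes a mean count and says nothing about the present proportion.

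**Structure.** Per arm, as shares of infants, let D = reported danger-sign episodes, a = share of D reaching care, and H = admissions without danger signs. On the Table 5.3 label, H sits in both parts of the fraction:

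E = (D·a + H) / (D + H)

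Care seeking for danger-sign illness is a. E equals a only when H = 0 or a = 1.

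**Inputs.** D = 0.20 (also 0.10), a = 0.70, H = 0.01 and 0.02. All are assumptions; the documents give none of them.

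**1. Only H differs; a is the same in both arms.**

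- D = 0.20, H = 0.02: (0.14 + 0.02)/0.22 = 0.727
- D = 0.20, H = 0.01: (0.14 + 0.01)/0.21 = 0.714
- Ratio 0.98, or 1.02 if the arms are exchanged.
- D = 0.10: 0.09/0.12 = 0.750 and 0.08/0.11 = 0.727. Ratio 0.97, or 1.03 exchanged.

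**2. Only recognition differs.** The SMS arm reports extra episodes in a share x of infants, of which a share s seeks care. With H = 0 to isolate this effect, the ratio is [(0.14 + x·s)/(0.20 + x)] / 0.70.

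| x | s | SMS arm | Ratio to 0.70 |
|---|---|---|---|
| 0.02 | 0.30 | 0.146/0.22 = 0.664 | 0.95 |
| 0.02 | 0.50 | 0.150/0.22 = 0.682 | 0.97 |
| 0.05 | 0.30 | 0.155/0.25 = 0.620 | 0.89 |
| 0.05 | 0.50 | 0.165/0.25 = 0.660 | 0.94 |

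The original episodes are attended at 70% throughout. Setting H = 0.01 in both arms leaves the extremes at 0.89 (0.165/0.26 against 0.15/0.21) and 0.97 (0.16/0.23 against 0.15/0.21). If the added episodes also attend at 70% and H = 0, the ratio is 1.00. The dilution therefore requires that added episodes be attended less often.

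**3. Power for the present endpoint.** With a control proportion of 70% and episodes in 10% or 20% of 2,250 infants (225 or 450 per arm), alpha 0.0045 and 80% power, the detectable SMS-arm proportion is about 84.5% or 80.6%. These too rest on assumed rates. They show only that the effective sample is the number of episodes, not the number of infants.

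**The case against.** The strongest reply has five parts.

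*The admission effect is small.* This stands. Log-binomial regression puts every success in the denominator, so the planned analysis yields the 2-3% shifts above, and only after a twofold difference in admissions is assumed. A reader might take the wording literally and add admissions to the numerator alone, which gives 0.15/0.16 = 0.94, or 0.08/0.09 = 0.89 at a 10% episode rate. The planned model cannot produce those figures.

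*More and milder reported episodes in the SMS arm are a hypothesis.* This stands. The SAP hypothesises better identification; nothing says milder, and prevention of illness is hypothesised as well. The denominator can change; the documents do not show that it will. A reader might go further and infer that the endpoint would signal harm while more infants are taken to care. In the second calculation care-seeking episodes do rise by 4-18% (0.146/0.14 to 0.165/0.14), but this treats each extra reported episode as new care. If mothers merely label more of the same illnesses, no additional infant is seen.

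*The protocol foresaw the problem.* In part. Protocol Section 15 warns that the control arm might show more visits or admissions and offers a severity comparison if so. That was written for the count outcome, is conditional, and does not appear in the SAP.

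*The changes were logged and forced by a data-collection error.* That explains one episode per report. It does not explain crediting admissions without danger signs, or setting aside the 2-week record. Eighteen weeks is an outer limit for late visits, and the documents do not show how often displacement would occur.

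*A remedy may exceed the data.* This also stands. Only the most recent episode was collected, and no section says that onset dates exist. The fix is limited accordingly.

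**Conclusion.** The point holds as a matter of definition: E departs from the attendance share a whenever H is above zero and a is below 1, and the denominator rests on unblinded reporting of signs that one arm is taught. The ratio can therefore move with no change in care seeking for a given illness. On the assumed rates the size is about 2-3% from admissions and up to about 11% (ratio 0.89-0.97) from recognition; the second range also needs added episodes to be attended less often than the rest.

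It would be too strong to say that the endpoint fails to address Aim 2b. A proportion conditional on illness does address care seeking for neonatal illness, but imperfectly. The 18-week window and the displacement of 2-week episodes weaken the match to the first 6 weeks by an amount that cannot be calculated from the documents. The stale power row is a documentation fault that leaves the endpoint without a stated detectable difference. This is one of 11 secondary endpoints; the primary outcome is unaffected.

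**What to change.** 1. Write out numerator and denominator. Use the same danger-sign episodes in both, with success defined as clinic attended or admitted. Report all admissions separately by arm. This removes the automatic successes but not the denominator problem.
2. For the denominator problem, add a sensitivity analysis over all live-born infants. State that it mixes illness incidence and labelling with care seeking, and captures only the most recent episode at each visit. Show it beside the main result, not in its place.
3. Use the most recent episode from both the 2-week and 6-week visits, clustered on mother, with a rule for the same illness reported twice. Table 5.3 already marks this row as log-binomial GEE, whereas Section 5.3 and Table 5.2 say log-binomial regression; make them agree.
4. Restrict to the first 6 weeks only if episode dates were recorded, keeping the 18-week version as a sensitivity analysis. If they were not, say so.
5. In Section 3c and Table 3.1, replace the clinic-visit figure with a detectable difference for the current proportion, or state that none was calculated.

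The cost is SAP wording, a logged amendment and one added model. No new data are needed, but the sponsor must first confirm whether episode dates exist and whether the two visits' reports can be told apart.
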